10.2. Accountability, Handling, and Disposal of Study Drugs

The investigator is responsible for drug accountability at the study site; however, some of the drug accountability duties may be assigned to an appropriate pharmacist or other designee. Inventory and accountability records must be maintained and readily available for inspection by the study monitor and are open to inspection at any time by any applicable regulatory authorities. The investigator or designee must maintain records that document:

- Delivery of study drugs to the study site.
- Inventory of study drugs at the site.
- Lot numbers and/or vial numbers (as applicable) of study drug used to prepare the infusion solution.
- Subject use of the study drugs including pill or unit counts from each supply dispensed.
- Return of study drugs to the investigator or designee by subjects.

The investigational product must be used only in accordance with the Protocol. The investigator will also maintain records adequately documenting that the subjects were provided the specified study drugs. These records should include dates, quantities, and any available batch or serial numbers or unique code numbers assigned to the investigational product and study subjects.

Completed accountability records will be archived by the site. The investigator or designee will be expected to collect and retain all used, unused, and partially used containers of study drugs until verified by the study monitor (unless otherwise agreed to by the sponsor). At the conclusion of the study, the investigator or designee will oversee shipment of any remaining study drugs back to the sponsor or its designee for destruction according to institutional standard operating procedures. If local procedures mandate on-site destruction of investigational supply, the site should (where local procedures allow) maintain the investigational supply until the study monitor inspects the accountability records in order to evaluate compliance and accuracy of accountability by the investigative site. At sites where the study drugs is destroyed before monitor inspection, the monitors rely on documentation of destruction per the site SOP.

10.3. Data Management

Data management will be performed in a validated database via an EDC system. All data entry, verification, and validation will be performed in accordance with the current standard operating procedures of the Data Management Department at the sponsor or its designee. The database will be authorized for lock once all defined procedures are completed.

The investigator will be provided with access to an EDC system so that an eCRF can be completed for each subject. Entries made in the eCRF must be verifiable against source documents; if updates to the database are not possible, any discrepancies should be explained and documented. The investigator will be responsible for reviewing all data and eCRF entries, and will sign and date the designated forms in each subject's eCRF, verifying that the information is true and correct. The investigator is responsible for the review and approval of all query responses.

Protocol deviations will be identified and recorded in the Protocol Deviation form of the eCRF. The study monitor will reference the Monitoring Plan in order to ensure that each issue identified is appropriately documented, reported, and resolved in a timely manner in accordance with the plan's requirements.

10.4. Data Privacy and Confidentiality of Study Records

The investigator and the sponsor or its designee must adhere to applicable data privacy laws and regulations. The investigator and the sponsor or its designee are responsible for ensuring that sensitive information is handled in accordance with local requirements (eg, Health Insurance Portability and Accountability Act of 1996). Appropriate consent and authorizations for use and disclosure and/or transfer (if applicable) of protected information must be obtained.

Subject names will not be supplied to the sponsor or its designee, if applicable. Only the subject number and subject's initials (subject's initials will only be recorded if allowable by local regulations) will be recorded in the eCRF, where permitted; if the subject's name appears on any other document (eg, laboratory report), it must be obliterated on the copy of the document to be supplied to the sponsor or its designee. Study findings stored on a computer will be stored in

accordance with local data protection laws. The subjects will be informed that representatives of the sponsor or its designee, IRB or IEC, or regulatory authorities may inspect their medical records to verify the information collected, and that all personal information made available for inspection will be handled in strictest confidence and in accordance with local data protection laws.

10.5. Financial Disclosure

Before study initiation, all clinical investigators participating in clinical studies subject to FDA Regulation Title 21 CFR Part 54 – Financial Disclosure by Clinical Investigators (ie, "covered studies") are required to submit a completed Clinical Investigator Financial Disclosure form that sufficiently details any financial interests and arrangements that apply. For the purpose of this regulation, "clinical investigator" is defined as any investigator or subinvestigator who is directly involved in the treatment or evaluation of research subjects, including the spouse and each dependent child of the clinical investigator or subinvestigator. These requirements apply to both US and foreign clinical investigators conducting covered clinical studies.

Any new clinical investigators added to the covered clinical study during its conduct must also submit a completed Investigator Financial Disclosure Form. During a covered clinical study, any changes to the financial information previously reported by a clinical investigator must be reported to the sponsor or its designee. At the conclusion of the covered clinical study, the clinical investigators will be reminded of their obligations. In the event that the clinical investigator is not reminded, they nevertheless will remain obligated to report to the sponsor or its designee any changes to the financial information previously reported, as well as any changes in their financial information for a period of 1 year after completion of the covered clinical study.

10.6. Publication Policy

By signing the study Protocol, the investigator and his or her institution agree that the results of the study may be used by the sponsor, Incyte Biosciences International Sàrl (Incyte), for the purposes of national and international registration, publication, and information for medical and pharmaceutical professionals. Study results will be published in accordance with applicable local and national regulations. If necessary, the authorities will be notified of the investigator's name, address, qualifications, and extent of involvement. The terms regarding the publication of study results are contained in the agreement signed with the sponsor or its designee. A signed agreement will be retained by the sponsor or its designee.

APPENDIX A. INFORMATION REGARDING EFFECTIVENESS OF CONTRACEPTIVE METHODS

For Subjects Participating in the Study:

The following methods that can achieve a failure rate of less than 1% per year when used consistently and correctly are considered as highly effective birth control methods.

Such methods include:

- Combined (estrogen and progestogen containing) hormonal contraception associated with inhibition of ovulation¹
 - oral
 - intravaginal
 - transdermal
- Progestogen-only hormonal contraception associated with inhibition of ovulation¹
 - oral
 - injectable
 - implantable²
- Intrauterine device (IUD)²
- Intrauterine hormone-releasing system (IUS)²
- Bilateral tubal occlusion²
- Vasectomized partner^{2,3}
- Sexual abstinence⁴

¹ Hormonal contraception may be susceptible to interaction with the IMP, which may reduce the efficacy of the contraception method.

² Contraception methods that in the context of this guidance are considered to have low user dependency.

³ Vasectomised partner is a highly effective method of avoiding pregnancy, provided that partner is the sole sexual partner of the female of childbearing potential trial participant and that the vasectomized partner has received medical assessment of the surgical success.

⁴ In the context of this guidance, sexual abstinence is considered a highly effective method only if defined as refraining from heterosexual intercourse during the entire period of risk associated with the study treatments. The reliability of sexual abstinence needs to be evaluated in relation to the duration of the clinical trial and the preferred and usual lifestyle of the subject.

Source: [CTFG 2014](#).

APPENDIX B. PROCEDURES AND SUPPORTIVE CARE GUIDELINES FOR SUBJECTS EXHIBITING IMMUNE-RELATED ADVERSE EVENTS

Immune-Related Adverse Event (irAE)	Supportive Care
Pneumonitis	
For Grade 2 (mild to moderate new symptoms):
 
 • Monitor symptoms daily and consider hospitalization. • Promptly start systemic steroids per institutional standard of care. • Consider adding prophylactic antibiotics for opportunistic infections in the case of prolonged steroid administration. • Re-imaging as clinically indicated. • If no improvement within 3 to 5 days, additional work-up should be considered, and prompt treatment with IV methylprednisolone should be started. • If still no improvement within 3 to 5 days despite IV methylprednisone, consider starting immunosuppressive therapy (eg, infliximab) after discussing with the medical monitor. 
Caution: Important to rule out sepsis and to refer to the infliximab label for general guidance before using infliximab.
 
 • Once improving, gradually taper steroids over ≥ 4 weeks and consider prophylactic antibiotics, antifungal, or anti-pneumocystis pneumonia (PCP) treatment (refer to current National Comprehensive Cancer Network [NCCN] Guidelines for treatment of cancer-related infections [Category 2B recommendation]). • Consider pulmonary and infectious disease consult. 
For Grade 3 or 4 (severe or new symptoms, new/worsening hypoxia, life threatening):
 
 • Promptly initiate empiric IV methylprednisolone or equivalent. • Carefully monitor subject and institute medical intervention as appropriate for the management of symptoms. Consider obtaining pulmonary and infectious disease consult. • If no improvement within 3 to 5 days, additional work-up should be considered, and prompt treatment with additional immunosuppressive therapy (eg, infliximab) should be started after discussing with the medical monitor. 
Caution: Rule out sepsis and refer to infliximab label for general guidance before using infliximab.
 
 • Once improving, gradually taper steroids over ≥ 4 weeks and consider prophylactic antibiotics, antifungals, and in particular, anti-PCP treatment (refer to current NCCN Guidelines for treatment of cancer-related infections [Category 2B recommendation]).

Immune-Related Adverse Event (irAE)	Supportive Care
Diarrhea/Colitis	
Note: Subjects should be carefully monitored for signs and symptoms of enterocolitis (eg, diarrhea, abdominal pain, and blood or mucus in stool, with or without fever) and of bowel perforation (eg, peritoneal signs and ileus).
 
For Grade 2 (mild to moderate new symptoms):
 
 • Consider symptomatic treatment, including hydration, electrolyte replacement, dietary changes (eg, American Dietetic Association colitis diet), and loperamide and/or budesonide. • Promptly start systemic steroids per institutional standard of care. • If event is not responsive within 3 to 5 days or worsens, GI consult should be obtained for consideration of further work-up, and prompt treatment with IV methylprednisolone should be started. • If still no improvement within 3 to 5 days, consider starting immunosuppressive therapy (eg, infliximab) after discussing with the medical monitor. 
Caution: Important to rule out bowel perforation and refer to infliximab label for general guidance before using infliximab.
 
 • Consult medical monitor if no resolution to \leq Grade 1 in 3 to 4 days. • Once improving, gradually taper steroids over \geq 4 weeks and consider prophylactic antibiotics, antifungals, and anti-PCP treatment (refer to current NCCN Guidelines for treatment of cancer-related infections [Category 2B recommendation]). 
For Grade 3 or 4 (severe or new symptoms, new/worsening diarrhea, life threatening):
 
 • Treatment with systemic corticosteroids should be initiated per institutional standard of care. • Manage symptoms and consider GI consult for further work-up as appropriate. • If still no improvement within 3 to 5 days, consider starting immunosuppressive therapy (eg, infliximab) after discussing with the medical monitor. 
Caution: Ensure GI consult to rule out bowel perforation and refer to infliximab label for general guidance before using infliximab.
 
 • Once improving, gradually taper steroids over \geq 4 weeks and consider prophylactic antibiotics, antifungals, and anti-PCP treatment (refer to current NCCN Guidelines for treatment of cancer-related infections [Category 2B recommendation]).

Immune-Related Adverse Event (irAE)	Supportive Care
Hepatitis	
For Grade 2 (mild to moderate new symptoms):
 
• Observe subject with regular and frequent checking of liver chemistries until improving or resolved.• Rule out non-irAE etiologies.• If event is persistent (> 3-5 days) or worsens, consider starting systemic steroids per institutional standard of care.• If still no improvement within 3 to 5 days, consider additional work-up and prompt treatment with IV methylprednisolone.• If still no improvement within 3 to 5 days, consider starting immunosuppressive therapy (eg, mycophenolate mofetil) after discussing with the medical monitor.• Infliximab should NOT be used.• Once improving, gradually taper steroids over ≥ 4 weeks and consider prophylactic antibiotics, antifungals, and anti-PCP treatment (refer to current NCCN Guidelines for treatment of cancer-related infections [Category 2B recommendation]). 
For Grade 3 or 4 (severe or new symptoms, new/worsening hepatitis, life threatening):
 
• Promptly initiate empiric IV methylprednisolone or equivalent.• If still no improvement within 3 to 5 days, consider starting treatment with immunosuppressive therapy (eg, mycophenolate mofetil) after discussing with the medical monitor.• Infliximab should NOT be used.• Consider hepatology consult for additional work-up, as appropriate.• Once improving, gradually taper steroids over ≥ 4 weeks and consider prophylactic antibiotics, antifungals, and anti-PCP treatment (refer to current NCCN Guidelines for treatment of cancer-related infections [Category 2B recommendation]).

Immune-Related Adverse Event (irAE)	Supportive Care
Dermatitis	
Note: Monitor subjects for signs and symptoms of dermatitis such as rash and pruritus. Unless an alternate etiology has been identified, signs or symptoms of dermatitis should be considered immune-mediated. If there is any bullous formation, the medical monitor should be contacted, and study treatment should be discontinued.
 
For Grade 2 (mild to moderate new symptoms):
 
• Consider dermatology consult.• Consider symptomatic treatment per institutional standard of care.• Consider moderate-strength topical steroid.• If no improvement of rash/skin lesions occurs within 3 to 5 days, or rash/skin lesions are worsening despite symptomatic treatment and/or use of moderate-strength topical steroid, discuss with medical monitor, and promptly start systemic steroids. 
For Grade 3 or 4 (severe or new symptoms, new/worsening dermatitis, life threatening):
 
• Consider dermatology consult.• Promptly initiate empiric IV methylprednisolone or equivalent.• Carefully monitor subject, and institute medical intervention as appropriate for the management of symptoms.• Consider hospitalization.• Once improving, gradually taper steroids over ≥ 4 weeks and consider prophylactic antibiotics, antifungals, and anti-PCP treatment (refer to current NCCN Guidelines for treatment of cancer-related infections [Category 2B recommendation]).• Discuss with medical monitor.

Immune-Related Adverse Event (irAE)	Supportive Care
Renal Failure or Nephritis	
Note: Subjects should be monitored for signs and symptoms that may be related to changes in renal function. Subjects should be thoroughly evaluated to rule out any alternative etiology. Steroids should be considered in the absence of clear alternative etiology, even for low-grade events (eg, Grade 2) in order to prevent potential progression to higher grade event.
 
For Grades 2 to 4:
 
• Carefully monitor subject and institute medical intervention as appropriate for the management of symptoms. Consider consult with nephrologist, if clinically indicated.• If event is persistent (> 3-5 days) or worsens, promptly start systemic steroids per institutional standard of care.• If event is not responsive within 3 to 5 days or worsens despite steroids, additional work-up should be considered, and prompt treatment with IV methylprednisolone started.• Once improving, gradually taper steroids over ≥ 4 weeks and consider prophylactic antibiotics, antifungals, and anti-PCP treatment (refer to current NCCN Guidelines for treatment of cancer-related infections [Category 2B recommendation]).

Immune-Related Adverse Event (irAE)	Supportive Care
Endocrinopathies	
Note: Subjects should be monitored for clinical signs and symptoms of hypophysitis, adrenal insufficiency (including adrenal crisis), and hyperthyroidism or hypothyroidism. Subjects may present with fatigue, headache, mental status changes, abdominal pain, unusual bowel habits, and hypotension, or nonspecific symptoms that may resemble other causes, such as brain metastasis or underlying disease. Unless an alternate etiology has been identified, signs or symptoms of endocrinopathies should be considered immune-mediated.
 
For Grade 2 (mild to moderate new symptoms):
 
 • In hypophysitis, treat with systemic corticosteroids per institutional standard of care. When symptoms improve to \leq Grade 1, steroid taper should be started and continued over ≥ 4 weeks. Replacement of appropriate hormones may be required as the steroid dose is tapered. 
Note: These suggested supportive care measures also apply to Grade 3 hypophysitis.
 
 • In hyperthyroidism, nonselective beta-blockers (eg, propranolol) are suggested as initial therapy. • In hypothyroidism, thyroid hormone replacement therapy with levothyroxine or liothyronine is indicated per standard of care. 
Note: Isolated hypothyroidism may be treated with replacement therapy without treatment interruption and without corticosteroids.
 
 • Evaluate endocrine function and, as clinically indicated, consider pituitary scan. • For subjects with abnormal endocrine work-up, except for those with isolated hypothyroidism, consider short-term, high-dose corticosteroids (eg, methylprednisolone or IV equivalent) and initiate appropriate hormone replacement therapy. • For subjects with normal endocrine work-up (eg, labs or magnetic resonance imaging [MRI]), repeat labs or MRI as clinically indicated. 
For Grade 3 or 4 (severe or new symptoms, new/worsening endocrinopathies, life threatening):
 
 • Hypothyroidism may be treated with replacement therapy without treatment interruption and without corticosteroids. • In hyperthyroidism, treat with an initial dose of IV corticosteroids followed by oral corticosteroids. Consider initiation of systemic corticosteroids at a dose of 1 to 2 mg/kg per day of prednisone or equivalent, and initiate appropriate hormone replacement therapy. Once improving, gradually taper immunosuppressive steroids over ≥ 4 weeks. • In hypophysitis, treat with an initial dose of IV corticosteroids followed by oral corticosteroids. When symptoms improve to \leq Grade 1, steroid taper should be started and continued over ≥ 4 weeks. Replacement of appropriate hormones may be required as the steroid dose is tapered. • For adrenal crisis, severe dehydration, hypotension, or shock: immediately initiate IV corticosteroids with mineralocorticoid activity. • Consult endocrinologist. • Consult medical monitor.

Immune-Related Adverse Event (irAE)	Supportive Care
Neuropathies	
Note: Monitor subjects for symptoms of motor or sensory neuropathy such as unilateral or bilateral weakness, sensory alterations, or paresthesia.
 
For Grade 2 (mild to moderate new symptoms):
 
• Consider systemic corticosteroids per institutional standard of care in addition to appropriate symptomatic treatment.• If no improvement within 3 to 5 days, consider additional work-up and treating with additional immunosuppressive therapy (eg, IV immunoglobulin G [IgG]) after discussing with the medical monitor. 
For Grade 3 or 4 (severe or new symptoms, new/worsening neuropathies, life threatening):
 
• Consider initiation of systemic corticosteroids (IV administration should be strongly considered) for severe neuropathies.• Institute medical intervention as appropriate for management of severe neuropathy.• If no improvement within 3 to 5 days despite IV corticosteroids, consider additional workup and treating with additional immunosuppressive therapy (eg, IV IgG) after discussing with the medical monitor.• Once stable, gradually taper steroids over ≥ 4 weeks.

**APPENDIX C. PROHIBITED MONOAMINE OXIDASE INHIBITORS
AND DRUGS ASSOCIATED WITH SIGNIFICANT
MONOAMINE OXIDASE INHIBITORY ACTIVITY**

Monoamine Oxidase Inhibitors	Drugs Associated With Significant Monoamine Oxidase Inhibitory Activity
Hydrazines (eg, phenelzine)	Meperidine
Caroxazone	Linezolid
Echinopsidine	Methylene blue
Furazolidone	
Tranlycypromine	
Brofaromine	
Metralindole	
Minaprine	
Moclobemide	
Pirlindole	
Toloxatone	
Lazabemide	
Pargyline	
Rasagiline	
Selegiline

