5.4.6. Criteria and Procedures for Dose Interruptions and Adjustments

Treatment with INCAGN01876 in combination with immune therapies may be delayed up to 4 weeks (ie, 28 days) to allow for resolution of toxicity. **If an interruption or discontinuation is necessary, all study treatments should be interrupted or discontinued.** Subjects may resume treatment if no medical condition or other circumstance exists that, in the opinion of the investigator, would make the subject unsuitable for further participation in the study. The treating investigator should contact the medical monitor to discuss the case of any subject whose treatment has been delayed for more than 4 weeks (ie, 28 days) before restarting treatment.

Instructions for dose interruptions and modifications for INCAGN01876 are outlined in [Table 7](#). Doses of epacadostat may be modified according to the guidelines and dose levels described in [Table 6](#). Individual decisions regarding dose interruptions and modifications of INCAGN01876 and epacadostat should be made using clinical judgment in consultation with the medical monitor (whenever possible), taking into account relatedness of the AE to the study treatment and the subject's underlying condition. Adverse events that have a clear alternative explanation,

or transient (≤ 72 hours) abnormal laboratory values without associated clinically significant signs or symptoms, may be exempt from dose-reduction rules.

Dose interruptions are permitted in the case of medical/surgical events or logistical reasons not related to study treatment (eg, elective surgery, unrelated medical events, subject vacation, and/or holidays). Subjects should be placed back on study treatment within 4 weeks (28 days) of the scheduled interruption, unless otherwise discussed with the medical monitor. The reason for interruption should be documented in the subject's source documentation.

Table 6: Dose Modifications for Epacadostat

Dose of Epacadostat	Dose Level -1	Dose Level -2 ^a
	First Reduction of Epacadostat	Second Reduction of Epacadostat
█████ BID	█████ BID	█████ BID

^a No more than 2 dose reductions are permitted for epacadostat.

Table 7: Criteria for Interruption and Restarting of Study Treatment

Toxicity	Hold Treatment for Grade	Agent	Timing for Restarting Treatment	Dose Level for Restarting Treatment	Treatment Discontinuation

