Hypothyroidism	N/A	Pembrolizumab	Therapy with pembrolizumab, INCAGN01876, and epacadostat can be continued while thyroid replacement therapy is instituted.	N/A	Therapy with pembrolizumab and epacadostat can be continued while thyroid replacement therapy is instituted.
		INCAGN01876			
		Epacadostat			
Infusion reaction	2	Pembrolizumab ^b	Toxicity resolves to Grade 0-1.	N/A	N/A
		INCAGN01876 ^b		Same dose level.	N/A
		Epacadostat		Same dose level.	N/A
	3-4	Pembrolizumab	Permanently discontinue.	N/A	Permanently discontinue.
		INCAGN01876			
		Epacadostat			

Table 7: Criteria for Interruption and Restarting of Study Treatment (Continued)

Toxicity	Hold Treatment for Grade	Agent	Timing for Restarting Treatment	Dose Level for Restarting Treatment	Treatment Discontinuation	
Pneumonitis	2	Pembrolizumab	Toxicity resolves to Grade 0-1.	N/A	Toxicity does not resolve within 12 weeks of last dose or inability to reduce corticosteroid to 10 mg or less of prednisone or equivalent per day within 12 weeks.	
		INCAGN01876		Reduce by 1 dose level		
		Epacadostat		Related: Reduce by 1 dose level. Not Related: Same dose level.		
	3-4 (or recurrent Grade 2)	Pembrolizumab	Permanently discontinue.	N/A		Permanently discontinue.
		INCAGN01876				
		Epacadostat				
Renal failure or nephritis	2	Pembrolizumab	Toxicity resolves to Grade 0-1.	N/A	Toxicity does not resolve within 12 weeks of last dose or inability to reduce corticosteroid to 10 mg or less of prednisone or equivalent per day within 12 weeks.	
		INCAGN01876		N/A		
		Epacadostat		Related: Reduce by 1 dose level. Not Related: Same dose level.		
	3-4	Pembrolizumab	Permanently discontinue.	N/A		Permanently discontinue.
		INCAGN01876				
		Epacadostat				
Rash	3 ^c	Pembrolizumab	Toxicity resolves to Grade 0-1.	Same dose level.	Toxicity does not resolve within 12 weeks of last dose or inability to reduce corticosteroid to 10 mg or less of prednisone or equivalent per day within 12 weeks.	
		INCAGN01876		Reduce by 1 dose level.		
		Epacadostat		Related: Reduce by 1 dose level. Not Related: Same dose level.		
	4	Pembrolizumab	Permanently discontinue.	N/A		Permanently discontinue.
		INCAGN01876				
		Epacadostat				

Table 7: Criteria for Interruption and Restarting of Study Treatment (Continued)

Toxicity	Hold Treatment for Grade	Agent	Timing for Restarting Treatment	Dose Level for Restarting Treatment	Treatment Discontinuation

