5.4.7. Management of Immune-Related Adverse Events

INCAGN01876, pembrolizumab, and epacadostat are considered immune modulators, and it is possible that irAEs (both nonserious and serious) may occur. Adverse events of a potential immunologic etiology, or irAEs, may be defined as AEs consistent with an immune phenomenon associated with drug exposure *after all other etiologies have been eliminated*. Immune-related AEs may be expected based on the nature of the study treatment, their mechanisms of action, and reported experience with these and other immunotherapies. Special attention should be paid to AEs that may be suggestive of potential irAEs. An irAE can occur shortly after the first dose or several months after the last dose of treatment. Suspected irAEs should be discussed with the medical monitor when possible.

Subjects should receive appropriate supportive care measures as deemed necessary by the treating investigator. Suggested supportive care measures for the management of treatment-related AEs with potential immunologic etiology are outlined in [Table 8](#). Detailed supportive care guidelines for specific irAEs can be found in [Appendix B](#). Pembrolizumab is an approved agent and has specific irAE management guidelines within the prescribing information; the treating investigator may use labeled guidance or institutional guidelines for the management of irAEs if preferred. For each AE, attempts should be made to rule out other causes, including, but not limited to, metastatic disease or bacterial or viral infection, which may require specific supportive care.

Table 8: Supportive Care Guidelines for Immune-Related Adverse Events

CTCAE Grade/Severity	Supportive Care ^a
Grade 1 (mild)	
 • Monitor symptoms and provide symptomatic treatment.
Grade 2 (moderate)	
 • Monitor symptoms and provide symptomatic treatment. • Consider consultation with specialists as necessary. • Consider systemic corticosteroids per institutional standard of care.

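### The stop for bullous rash appears only in Appendix B, while the Table 7 Rash row allows all three drugs to be restarted after Grade 3 rash

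*Protocol*

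**What the plan says.** **Appendix B, Dermatitis (opening note).** "If there is any bullous formation, the medical monitor should be contacted, and study treatment should be discontinued". The note is not tied to a grade and gives no condition for restarting.

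**Section 5.4.6.** "Instructions for dose interruptions and modifications for INCAGN01876 are outlined in" Table 7. The section treats interruption and discontinuation as separate actions that apply to the whole regimen: "If an interruption or discontinuation is necessary, all study treatments should be interrupted or discontinued".

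**Table 7, Rash row.** At Grade 3, treatment is held and the restart condition is "Toxicity resolves to Grade 0-1". Pembrolizumab restarts at the same dose and INCAGN01876 one level lower. Epacadostat restarts one level lower if the rash is related, and otherwise at the same level. The Grade 3 discontinuation column covers only rash that has not resolved, or steroids that cannot be brought down to 10 mg of prednisone or equivalent, within 12 weeks. At Grade 4 the instruction is "Permanently discontinue".

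**Table 7, footnote c.** Grade 3 rash needs no hold if there is no desquamation, no mucosal involvement and no need for systemic steroids, and it settles to Grade 1 within 14 days. Bullae are not among the conditions.

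**Section 5.4.7 and Table 8.** Appendix B is presented as detailed supportive care guidance. The investigator may prefer the pembrolizumab label or institutional guidelines for managing immune-related events.

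**Section 5.4.10.** The list of permanent stops names Grade 2 or higher ocular immune-related events, among others. It does not name bullous formation.

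**The concern.** A stopping instruction for a skin reaction sits in one sentence of a supportive-care appendix. It is absent from the two places where a site would look for stopping rules: the dosing table and the list of permanent stops. Other special stops are placed there: recurrent Grade 2 pneumonitis is in Table 7, and ocular events are in Section 5.4.10.

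A site that doses from Table 7 could therefore restart a subject after a Grade 3 blistering rash, or under footnote c not hold at all, when Appendix B says to stop. What is at stake is the safety of an individual subject and consistent handling across sites. No statistical property of the design is involved.

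**Working it through.** No arithmetic applies. The check is a side-by-side reading, followed by a search for any text that settles precedence.

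**By grade, for a rash with bullae:**

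| Rash grade | Appendix B note | Table 7 Rash row | Result |
|---|---|---|---|
| 1 | Stop | No entry | Table 7 silent |
| 2 | Stop | No entry | Table 7 silent |
| 3 | Stop | Hold, may restart at Grade 0-1 | Texts diverge |
| 4 | Stop | Permanent stop | Texts agree |

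So the texts diverge at 1 grade, Table 7 is silent at 2, and they agree at 1 (1 + 2 + 1 = 4). At Grade 3, Table 7 gives a restart dose for 3 of 3 drugs.

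**Test case 1.** A Grade 3 rash with bullae resolves to Grade 1 within 4 weeks, and steroids come down to 10 mg or less within 12 weeks. Under Table 7, neither discontinuation condition is met and all three drugs may restart. Under Appendix B, study treatment stops.

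**Test case 2.** A Grade 3 rash with bullae meets every condition of footnote c. Under Table 7, no hold is needed. Under Appendix B, study treatment stops. A site following Appendix B would rarely reach this case, because the appendix calls for prompt intravenous steroids at Grade 3 or 4 and footnote c requires that systemic steroids are not needed. A site using other guidelines could reach it.

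**Is there a tie-break?**

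- Section 5.4.6 gives Table 7 the dosing role and leaves individual decisions to clinical judgment. It does not rank the table against the appendix.
- Section 5.4.7 and the Table 8 footnote send readers to Appendix B for supportive care. Section 5.4.7 also allows other guidelines instead.
- Table 8 says only that treatment may be stopped permanently for clinically significant or severe immune-related events.
- Section 5.4.10 has a general criterion for related events judged not to be in the subject's interest, and Section 5.5.1 requires withdrawal where the investigator judges continuing injurious. Both depend on judgment.

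None of these says which instruction prevails for bullous rash.

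**The case against.** The strongest reply is that this is a general rule plus a specific stop, and that both can be obeyed. Table 7 sets the condition for restarting but does not require it. Section 5.4.6 says: "Subjects may resume treatment if no medical condition or other circumstance exists that, in the opinion of the investigator, would make the subject unsuitable". Stopping for bullae under Appendix B breaches nothing in Table 7, and the usual reading that the specific overrides the general favours the appendix. This stands, and it rules out a stronger reading that a reader might infer, namely that the protocol directs sites to rechallenge after a bullous reaction.

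The routing and safeguards are also real. Table 8 refers to Appendix B, and the dermatitis note presumes an immune cause unless another is found. The note itself calls for contact with the medical monitor without qualification. Section 5.4.7 adds: "Suspected irAEs should be discussed with the medical monitor when possible". These lower the risk. They do not put the stop in Table 7 or Section 5.4.10, and a site that has chosen other guidelines may never read the note.

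A reader might also argue that the appendix's word for stopping could mean a hold, since Table 15 lets some subjects restart after treatment is discontinued. That table concerns radiologic progression, not toxicity, and Section 5.4.6 separates interruption from discontinuation. Reading the note as a hold is strained. If it were accepted, it would also remove most of the divergence at Grade 3.

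Finally, Section 5.4.1 tells investigators to follow the pembrolizumab label, which may contain its own stop. The label is not in these documents, so it cannot be shown that sites had no other stopping rule, or that they had one.

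**Conclusion.** The point holds as a minor safety inconsistency. Appendix B stops treatment for any bullous formation. The table that the protocol designates for dosing allows all three drugs to restart after Grade 3 rash, its footnote c does not exclude bullae, and Section 5.4.10 is silent. The Appendix B stop is the better reading, but it can be missed.

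The divergence is confined to Grade 3. A reader might extend it to Grades 1-2, but Table 7 has no entry there and contradicts nothing. A reader might also estimate how many subjects were affected from the 3% severe skin reaction rate given in Section 1.3.2 for epacadostat plus pembrolizumab. The documents do not support that: they give no rate of bullous rash and no rate for the triplet. Exposure was small in any case. SAP Section 10.1.1.2 reports limited enrolment in Treatment Group C and none in Groups B and D. Nothing in the documents shows that a subject was restarted after a bullous rash.

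The conclusion assumes that the Appendix B note means a stop without restart, and it assumes nothing about the label. Sample size, alpha and power are unaffected.

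**What to change.** Make three wording changes in the protocol:

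1. Add to the Table 7 Rash row: *any grade with bullous formation: contact the medical monitor and permanently discontinue all study treatment (see Appendix B)*.
2. Exclude bullous rash from the exemption in footnote c.
3. List bullous formation in Section 5.4.10.

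The cost is an amendment to the text, with no added visits, assessments or subjects. The downside is that a subject with mild blistering loses the option to restart, which the Appendix B note already implies. Because enrolment has stopped, the benefit is limited to any subject still on treatment (the documents do not say how many) and to later protocols that reuse this text.
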